9.6.2 Primary Efficacy Endpoint

The primary objective of the trial is to demonstrate that MENOPUR[®] is non-inferior to recombinant FSH with respect to ongoing pregnancy rate in a single fresh treatment cycle following a GnRH antagonist protocol. Ongoing pregnancy is defined as presence of at least 1 intrauterine pregnancy with a detectable fetal heartbeat at 10-11 weeks gestation (8-9 weeks after blastocyst transfer in the fresh cycle). The non-inferiority limit for the difference between treatments (MENOPUR[®] versus Gonal-f[®]) is -12% (absolute). The non-inferiority hypothesis to be tested for the primary endpoint is:

$$H_0$$
: $\pi_{MENOPUR}$ - $\pi_{Gonal-f}^{\otimes} \leq -12\%$

against the alternative

$$H_1$$
: $\pi_{MENOPUR}$ - $\pi_{Gonal-f}^{\otimes} > -12\%$,

where $\pi_{MENOPUR}$ and $\pi_{Gonal-f}^{@}$ denote the ongoing pregnancy rate of subjects randomized and treated with MENOPUR and Gonal-f , respectively, in a single fresh embryo transfer following a GnRH antagonist protocol.

The null hypothesis (H₀) will be tested against the alternative by constructing a 2-sided 95% confidence interval for the difference in ongoing pregnancy rates. If the lower-limit of the 95% confidence interval is greater than the non-inferiority limit (-12%), the null hypothesis will be

Date: 10 Dec 2015 E-Protocol Amendment-19588; Ver. 1.0 Supersedes: 28 October 2015 Page 52 of 69

rejected and it would be claimed that MENOPUR® is non-inferior to Gonal-f® with respect to ongoing pregnancy rate in a single fresh embryo transfer following a GnRH antagonist protocol.

If the 95% confidence interval for the treatment difference not only lies above the non-inferiority limit (-12%) but also above zero then there is evidence of superiority in terms of statistical significance at the 2-sided 5% level. With evidence of superiority, the corresponding 2-sided p-value will be reported. There is no need for a multiplicity adjustment since it is a simple closed test procedure.

Due to the expected large sample size, the confidence interval will be established based on the asymptotic normal distribution as follows:

$$\hat{\pi}_{\textit{MENOPUR}} - \hat{\pi}_{\textit{Gonal-}f} \pm Z_{(1-\alpha/2)} \sqrt{\frac{\hat{\pi}_{\textit{MENOPUR}}(1-\hat{\pi}_{\textit{MENOPUR}})}{N_{\textit{MENOPUR}}} + \frac{\hat{\pi}_{\textit{Gonal-}f}(1-\hat{\pi}_{\textit{Gonal-}f})}{N_{\textit{Gonal-}f}}}$$

where

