STATISTICAL ANALYSIS PLAN

A Randomized, Assessor-blind Trial Comparing MENOPUR® (menotropins for injection) and Recombinant FSH (Follicle Stimulating Hormone) in a GnRH Antagonist Cycle with Single-Blastocyst Transfer in a High Responder Subject Population

000205

Investigational Product:	MENOPUR® (menotropins for injection)
Indication:	Development of multiple follicles and pregnancy in ovulatory women as part of an Assisted Reproductive Technology (ART) Cycle with ICSI
Phase:	4
Author:	[name]
Date of issue:	March 8, 2017
Version:	4.0

The information in this document is confidential and is proprietary to Ferring Pharmaceuticals A/S or another company within the Ferring Group. It is understood that information in this document shall not be disclosed to any third party, in any form, without prior written consent of an authorised officer of Ferring Pharmaceuticals A/S or another company within the Ferring Group

Change log

Version No.	Effective Date	Reason for the Change / Revision	Supersedes

2.0	21SEP2015	SAP based on Protocol dated 22JUL2015	Version 1
3.0	16Feb2017	
For some baseline characteristics the analysis based on the safety population has been removed. The summaries based on the mITT and PP populations were considered to be sufficient.For the primary analysis, the sensitivity analysis based on ITT population was removed. Furthermore, sub-group analysis by genetic testing was added.Clarification on protocol deviation analysis.Added forest plots and boxplots.Removed the logistic regression.Other minor clarification and corrections were made.	Version 2
4.0		
In the conduct of the study, it was observed that there were a number of patients that had their primary endpoint visit too early (up to 4 weeks early). Initially, it was planned to use the visit assessment for this analysis however, because of this observation visit windows were considered to be a more accurate assessment for the endpoint. In Section 9, the visit window has now been defined. Furthermore, if a patient has pregnancy assessment beyond this visit she will also be considered as responder.
 
To make it consistent, this type of window was also applied to the clinical pregnancy endpoint.
	Version 3

Author, Reviewers, and Approver of the Statistical Analysis Plan

Author: [name].
Senior Project Statistician, Biometrics
Ferring International Pharmascience Center US, Inc.

Reviewers: [name].
Vice President, Reproductive Health & Urology

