9.1.3 Handling of Drop-Outs and Missing Values

For the primary and secondary endpoints positive β -hCG and clinical pregnancy missing observations will be imputed to negative unless a positive result is observed at a later pregnancy assessment. For example, if the outcome of β -hCG is missing but clinical pregnancy is 'positive' then β -hCG will be imputed as 'positive'.

Missing values will not be imputed for the any of the other secondary endpoints.

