$\hat{\pi}_{Gonal-f}$: is the observed ongoing pregnancy rate of subjects randomized to Gonal-f® in a single fresh treatment cycle following a GnRH antagonist protocol.

$N_{MENOPUR}$: is the number of subjects randomized to MENOPUR®.

$N_{Gonal-f}$: is the number of subjects randomized to Gonal-f®.

$Z_{(1-\alpha/2)}$: is the 1- $\alpha/2$ percentile in the standard normal distribution.

α : is the significance level, i.e., 0.05.

Subjects who do not have at least 1 intrauterine pregnancy with a detectable fetal heartbeat at 10–11 weeks gestation (8-9 weeks after blastocyst transfer in the fresh cycle) due to missing data, early withdrawal, or any other reason will be considered treatment failures (i.e., not having ongoing pregnancy) unless they have an assessment of detectable fetal heartbeat at a later date. Hence, for the analysis of this endpoint all positive (detectable fetal heartbeat) ultrasound assessments that occur in the interval from the end of 7th week from fresh transfer till the end of study will be considered as responder for the primary endpoint (i.e., ultrasound assessment date – fresh transfer date + 1 \geq 7 *7 = 49). Forty nine days was used because the 8-9 weeks visit window included 50

(beginning of the 8th week) to 63 days after fresh transfer. The primary endpoint analysis will be based on the mITT analysis set.

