10.5.2 Signs of Excessive Response

A table will be prepared summarizing signs of excessive response. The table will present the number of subjects in following categories:

- OHSS early onset defined as at most 9 days after hCG administration
- Cancellation of cycle due to excessive response
- Preventive action (leuprolide acetate)
- Received a medical or surgical intervention for OHSS

11 Interim analyses

No interim analysis is planned.

12 Deviations from protocol analysis

For some of the baseline characteristics, the analysis based on the safety population has been removed. The summaries based on mITT and PP populations were considered to be sufficient.

For the primary analysis, the sensitivity analysis based on ITT populations was removed. Furthermore, sub-group analysis by genetic testing was added.

For the primary analysis, it was added that patients that have positive pregnancy test at any time after the 8-9 week window post-fresh transfer will also be considered as positive for this primary endpoint.

13 References

14 Tables, Listings and Figures Shells

The document with tables, figures and listings (TLF) shells presented in a separate document.

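### SAP 9.2 accepts a heartbeat scan on day 49 as ongoing pregnancy, although the window it cites as its reason runs from day 50 to day 63

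*SAP*

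**What the plan says.** Protocol 9.6.2 defines ongoing pregnancy as an intrauterine pregnancy with a "detectable fetal heartbeat at 10-11 weeks gestation (8-9 weeks after blastocyst transfer in the fresh cycle").

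SAP 9.2 repeats that definition. It then treats a subject without such a finding as a failure "unless they have an assessment of detectable fetal heartbeat at a later date". From this it derives the working rule: positive ultrasound assessments "in the interval from the end of 7th week from fresh transfer till the end of study will be considered as responder". The rule is written as scan date − fresh transfer date + 1 ≥ 7 × 7 = 49. The reason follows: "Forty nine days was used because the 8-9 weeks visit window included 50", continued as "beginning of the 8th week) to 63 days after fresh transfer".

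For incomplete data, SAP 9.1.3 says that "missing observations will be imputed to negative unless a positive result is observed at a later pregnancy assessment". No sentence there or in 9.2 addresses a loss or a negative scan after an earlier positive.

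SAP 9.3.2 builds clinical pregnancy the same way: a formula of ≥ 14 beside a window of days 15 to 28. It places that assessment at 5-6 weeks of gestation, 3-4 weeks after transfer. Protocol 2.2 places it at 6-7 weeks, 4-5 weeks after transfer.

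The version 4.0 change log explains that some subjects had the endpoint visit up to four weeks early. It adds "In Section 9, the visit window has now been defined", without giving a day. SAP section 12 (Deviations from protocol analysis) records only that subjects with a "positive pregnancy test at any time after the 8-9 week window post-fresh transfer will also be considered as positive for this primary endpoint". The one sensitivity analysis in SAP 9.2.1 that repeats the primary comparison in another analysis set is the per-protocol (PP) analysis, run in the same way as the main one.

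**The concern.** The formula decides who is a responder in the non-inferiority test, and it disagrees with the sentence written to justify it. A scan on day 49 qualifies under the formula and lies outside the stated window.

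The rule is also open-ended in one direction only. A later positive can rescue a missing result, but nothing removes an early positive if the pregnancy is then lost. Read literally, a subject with a heartbeat just before the window and a loss before it opens counts as having an ongoing pregnancy. She would then either leave the early-loss endpoint of SAP 9.3.3 or be counted both as a responder and as an early loss, depending on which variable 9.3.3 uses.

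This is not a remote case, because the change log itself records early endpoint visits. The PP analysis applies the same responder rule. Exclusions for visit non-compliance (SAP section 5) may remove some early scans, but nothing ensures it.

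**Working it through.** **Inputs.** The formula, the cut-off of 49 and the window of days 50 to 63 come from SAP 9.2. The cut-off of 14 and the window of days 15 to 28 come from SAP 9.3.2. The two-week gap between transfer and gestational age comes from the endpoint definition (8-9 weeks after transfer = 10-11 weeks of gestation). About 600 subjects, 1:1, gives 300 per arm.

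**1. The SAP's own window.** The + 1 makes the transfer date day 1. Week k then covers days 7(k − 1) + 1 to 7k. Week 7 is days 43-49, week 8 is days 50-56 and week 9 is days 57-63. Weeks 8-9 are therefore exactly days 50-63, so the stated window reproduces.

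**2. The formula against that window.** The first qualifying scan is day 49, which is 48 elapsed days and the last day of week 7. The gap is 50 − 49 = 1 day on the same count. If the window is in elapsed days, it is 50 − 48 = 2 days. Neither reading makes the two agree. In SAP 9.3.2 the gap is 15 − 14 = 1 day in the same way.

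**3. Gestational age** (elapsed days + 14, with elapsed = day − 1):

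| Day | Elapsed | Completed | Ordinal week |
|---|---|---|---|
| 49 | 48 | 62 d = 8w6d | 9th |
| 50 | 49 | 63 d = 9w0d | 10th |
| 56 | 55 | 69 d = 9w6d | 10th |
| 57 | 56 | 70 d = 10w0d | 11th |
| 63 | 62 | 76 d = 10w6d | 11th |

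- *Ordinal weeks:* days 50-63 are exactly the 10th and 11th weeks. This matches the SAP's description of day 50 as the start of the 8th week, so only day 49 comes too early.
- *Completed weeks:* 8 full weeks after transfer plus 2 is 10w0d, a plain reading of the protocol's words. Days 49 to 56 come before it: 56 − 49 + 1 = 8 days.
- *Different dating (assumption, not in the documents):* with elapsed + 19 days, day 49 is 67 d = 9w4d and 10w0d falls on day 52. That leaves days 49-51 early in completed weeks and none in ordinal weeks.

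The range is thus 0 to 8 admitted days, depending on a convention that the SAP does not state.

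**4. Clinical pregnancy.** On the two-week gap, day 15 is 14 + 14 = 28 d = 4w0d (5th week) and day 28 is 27 + 14 = 41 d = 5w6d (6th week). The window fits 5-6 weeks in ordinal weeks, and day 14 (3w6d) falls outside it. The protocol's 4-5 weeks after transfer would be days 22-35 on the same count, one week later.

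**5. Effect on the primary comparison.** One subject is 1/300 = 0.33 points (1/275 = 0.36 points). As a one-sided illustration, assume 300 per arm, 50% in both arms, and responders reclassified as failures in the MENOPUR arm only. The lower 95% limit is −8.0% with none reclassified, −10.0% with 6, −11.99% with 12 and −12.3% with 13. Reclassification balanced across arms would move it much less. The sample size does not depend on the rule.

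**The case against.** The strongest reply is that the rule is explicit and can be programmed. The formula, the product 7 × 7 and the phrase about the end of the 7th week all agree on 49; only the explanatory sentence points to 50. Read literally, any positive scan from then on wins. This stands, so a reader who inferred that two programmers must classify subjects differently would be going too far.

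Second, on the ordinal reading the exposure is a single day. The version 4.0 window replaced a plan to use the visit assessment as recorded, so it is stricter about early scans than what it replaced. That also stands. It limits the size of the problem but does not remove the mismatch, and the completed-week reading remains open.

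Third, one might want any loss up to the end of 10-11 weeks to cancel an earlier heartbeat. The documents do not support that. A subject with a heartbeat on day 52 and a loss on day 62 has met the endpoint on the SAP's count, and making her a failure would change the endpoint. The precedence statement must therefore concern only scans before the window opens.

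Fourth, the change is disclosed: the change log says that a window was defined and why, and SAP 9.2 gives the day. This is fair. What is missing is the lower bound in section 12; the reference there to a pregnancy test is an editorial slip. The natural reading of SAP 9.3.3 is also that it uses the 9.2 variable, but the SAP should say so.

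**Conclusion.** The cut-off in SAP 9.2 is inconsistent with its own stated window by one day on the SAP's count, or by two if the window is in elapsed days. SAP 9.3.2 repeats the slip and also departs from the protocol's weeks. A pregnancy lost before the window opens can count as ongoing only if it had a positive scan on an admitted early day. That means day 49 on the reading the SAP's wording suggests, and days 49-56 if completed weeks are meant, both on the documents' two-week gap.

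A reader might infer that losses before 10-11 weeks are widely counted as successes, or that the rule favours non-inferiority. The documents support neither. They give no number of affected subjects and no split by arm, and the rule applies equally to both arms. The error is small in days, but it sits in the definition of the primary endpoint and is easy to correct.

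**What to change.** (a) Change the SAP 9.2 formula to ≥ 50 on its existing count. Reconcile the 9.3.2 formula with its own window, and that window with the protocol's.

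(b) State that a positive scan before the window opens does not count, that a heartbeat inside the window meets the endpoint, and that early pregnancy loss is derived from the same variable.

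(c) List the lower bound in section 12, and refer there to a detectable fetal heartbeat, as 9.2 does.

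(d) Add one sensitivity analysis requiring a heartbeat at or after 10 completed weeks, with the dating convention stated. Report by arm how many subjects are classified differently.

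The cost is SAP wording, a corrected derivation and one extra table on data already collected. The downside is that a viable pregnancy scanned only on day 49 becomes a failure in the primary analysis, and one scanned only before 10 completed weeks becomes a failure in the sensitivity analysis. The count by arm would show how many there are.

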9.2.1 Sensitivity Analyses

Sensitivity analyses for the primary endpoint analysis will be conducted for the PP analysis set in the same manner as the mITT analysis set.

In addition, the ongoing pregnancy rate will be presented by center for the mITT analysis set, for subjects in the mITT analysis set with oocytes retrieved, and for subjects in the mITT analysis set with an embryo transfer.

Furthermore, the ongoing pregnancy rate will be presented for the following break downs for all mITT subjects, for mITT subjects with oocytes retrieved and for mITT subjects with a blastocyst transfer:

- By reason for infertility
- By center
- By number of oocytes retrieved (<=3, 4-7, 8-10, 11-14, >=15)
- By quality of blastocyst transferred.
- By AMH level at screening
- For patients that received fresh blastocyst, by results of the genetic testing

For these sub-group analyses, treatment differences and associated 95% CIs will be generated. Furthermore, these summaries will be displayed in a forest plot.

9.3 Secondary Endpoints

All secondary endpoints will be based on the mITT analysis set unless otherwise specified. Positive β-hCG rate and clinical pregnancy rate, in the fresh cycle, will be presented by treatment group with the corresponding 95% confidence intervals of the treatment difference. This will be calculated in the same manner as the primary endpoint.

9.3.1 Positive β-hCG rate in the fresh cycle

Positive β-hCG in the fresh cycle is defined as 2 positive β-hCG tests; the first performed approximately 10-14 days after the fresh blastocyst transfer with a second positive test at least 2 days later. The positive β-hCG rate in the fresh cycle will be presented by treatment group with the corresponding 95% confidence intervals of the treatment difference. This analysis will also be repeated for the PP set.

Subjects who do not have 2 positive β-hCG tests due to missing data, early withdrawal, or any other reason will be counted as not having positive β-hCG unless a positive result is observed at a later pregnancy assessment. For example, if the outcome of β-hCG is missing but clinical pregnancy is 'positive' then β-hCG will be imputed as 'positive'.

9.3.2 Clinical pregnancy rate in the fresh cycle

Clinical pregnancy in the fresh cycle is defined as at least 1 intrauterine gestational sac, confirmed by TVUS, with a fetal heart beat at 5-6 weeks gestation (3-4 weeks after the fresh blastocyst transfer). The clinical pregnancy rate in the fresh cycle will be presented by treatment group with the corresponding 95% confidence intervals of the treatment difference. This analysis will also be repeated for the PP set.

Subjects who do not have at least 1 intrauterine gestational sac, confirmed by TVUS, with a fetal heart beat at 5-6 weeks gestation (3-4 weeks after the fresh blastocyst transfer) due to missing data, early withdrawal, or any other reason will be counted as not having clinical pregnancy unless a positive result is observed at a later pregnancy assessment. For example, if TVUS test at 5-6 weeks is missing but clinical pregnancy is 'positive' at 10-11 weeks of gestation, it will be imputed as 'positive'. Hence, for the analysis of this endpoint all positive (detectable fetal heartbeat) ultrasound assessments that occur in the interval from the end of 2nd week from fresh transfer till the end of study will be considered as responder for this secondary endpoint (i.e., ultrasound assessment date – fresh transfer date + 1 \geq 2 * 7 = 14). Fourteen days was used because the 3-4 weeks visit window included 15 (beginning of the 3th week) to 28 days after fresh transfer.

9.3.3 Early pregnancy loss in the fresh cycle

Early pregnancy loss in the fresh cycle is defined as 2 positive β -hCG tests, but no ongoing pregnancy at 10-11 week's gestation, in the fresh cycle. The early pregnancy loss rate in the fresh cycle will be calculated for mITT subjects with 2 positive β -hCG tests and presented by descriptive statistics for each treatment group. Furthermore, the difference in event rates between the two treatments will be presented together with the associated 95% CI.

9.3.4 Follicles

The follicles within each treatment group on stimulation day 6 and last day of stimulation will be summarized by frequency at the follicle level (i.e. the number of follicles within the treatment group that are \leq 9mm, 10-11 mm, 12-14 mm, 15-16 mm, and \geq 17 mm). The follicles for each subject within each treatment group on stimulation day 6 and last day of stimulation will also be summarized by the largest follicle size, average follicle size, average size of the 3 largest follicles, and the rate of follicles \geq 17 mm, \geq 15 mm, and \geq 12 mm. Tables will be produced for all mITT subjects and for all mITT subjects with oocytes retrieved.

9.3.5 Endocrine Profile

The endocrine profile will be summarized using descriptive statistics by scheduled visit, as well as for the change from baseline for post-baseline visits;

- Serum follicle-stimulating hormone (FSH), hCG, luteinizing hormone (LH), androstenedione, total testosterone, dehydroepiandrosterone will be summarized on Day 1, Day 6, and last day of stimulation.

- Progesterone (P4), estradiol (E2) will be summarized on Day 1, Day 6, last day of stimulation, and Visit 4 (morning following hCG trigger)

Any subject who receives an antagonist earlier than Day 6 will be excluded from Day 6 endocrine analysis. Associated box-plots will also be generated.

9.3.6 Oocytes

The number of oocytes retrieved, the number of metaphase II oocytes, the number of oocytes undergoing ICSI, and the number of normally fertilized (2PN) oocytes will be summarized by frequency distribution and by descriptive statistics for each treatment group.

9.3.7 Fertilization Rate

The fertilization rate will be expressed as a percentage for each subject and calculated as 100 times the ratio of the number of fertilized 2PN oocytes to the number of oocytes retrieved. In addition for subjects undergoing ICSI the fertilization rate will be expressed as a percentage for each subject and calculated as 100 times the ratio of the number of fertilized 2PN oocytes to the number of metaphase II oocytes. Descriptive statistics will be provided by treatment group.

9.3.8 Quality of Embryos 3 Days after Oocyte Retrieval

The quality of embryos 3 days after oocyte retrieval will be assessed by cleavage stage, blastomere uniformity, cell size, the degree of fragmentation, and visual signs of multinucleation. Frequency distributions and descriptive statistics will be provided for each treatment group at the embryo level.

9.3.9 Quality of Blastocysts 5 Days after Oocyte Retrieval

The quality of blastocysts 5 days after oocyte retrieval will be assessed by blastocyst expansion and hatching status, blastocyst inner cell mass grading, and trophectoderm grading. Blastocyst information collected on day 6 and 7 will be summarized similarly. Furthermore, the overall quality of the blastocysts on day 5 will also be summarized. Frequency distributions will be provided for each treatment group at the blastocyst level.

